#### **7.3.2 Recurrence Medication**

If the migraine responds within 2 hours (headache becomes pain free) but then recurs after 2 hours, a second dose of randomized study drug may be taken up to 24 hours after the first dose.

## 7.4 Prohibited Medications

Use of the following medications is prohibited for the duration of a subject's participation in the study from **Screening/Visit 1** through **EoS/Visit 2**:

- Any investigational treatment other than lasmiditan.
- All other symptom modifying treatments (e.g. antiemetics) for migraine except rescue or recurrence medication as detailed in [Section 7.3.1](#) and [7.3.2](#).
- If a patient requires the initiation of migraine prophylaxis (concomitant medication to reduce the frequency of migraine episodes) or a change in ongoing migraine prophylaxis after the **Screening/Visit 1** they should be withdrawn from the study.

## 7.5 Treatment Compliance

Study drug will be taken by the subject at home throughout the study. Prior to discharge from **Screening/Visit 1** subjects will be given study drug to treat a single migraine attack and a second dose for rescue or recurrence. Information on the time and date of each dose (initial treatment along with the use of rescue medication or treatment of recurrence) will be recorded by the subject in the electronic diary. Subjects will be instructed to return all unused study drug to the clinic at **EoS/Visit 2**.

## 7.6 Randomization and Blinding

Subjects will be randomized through a central randomization process by IRT during **Screening/Visit 1**. A randomization number and study drug card number will be assigned for dosing. Lasmiditan and matching placebo will be provided in double-blinded treatment packs.

## 7.7 Unblinding Procedures

### 7.7.1 Emergency unblinding of treatment assignment

Emergency unblinding should only be performed when necessary in order to treat the subject. There is no known antidote to lasmiditan, so symptomatic and supportive management of any suspected and treatment related adverse event, if necessary, is clinically indicated.

Unblinding will result in the subject being discontinued from the study, irrespective of whether the Investigator ultimately agrees with the event being related to study drug (lasmiditan). Most often, study drug discontinuation and knowledge of the possible treatment assignments are sufficient to treat a study subject who presents with an emergency condition. The Investigator will have the ability to break the blind for any subject through the centralized randomization system (IRT). However, the Investigator should make every effort to contact the Sponsor's medical monitor or their designee to discuss the subject's emergency situation and the need to unblind prior to unblinding any subject, but must contact the Sponsor or designee within one working day after the event occurs. The Sponsor's medical monitor or their designee will also have the ability to break the blind for the Investigator while remaining blinded via the centralized randomization system if the treating Investigator requests this. The blind may be broken in the case of a pregnancy should the subject desire this information. Any subject for whom the blind is broken is to be discontinued from future study treatment. The date, time and reason for breaking the blind are to be recorded in the subject's source documents.

### 7.7.2 Unblinding for Regulatory Authorities

In cases where unblinding is required for the purposes of reporting expedited safety events to country specific regulatory agencies or Ethics Committees, the unblinding will be performed by

an authorized member of the Quintiles Pharmacovigilance team. A blinded version of any documents to be submitted to the authorities will be shared as appropriate with study staff and site personnel. Only the authorized person(s) within the Quintiles Pharmacovigilance and Regulatory Affairs will have access to the unblinded version of any documents. The procedures for requesting and obtaining unblinded information and for maintaining the integrity of the data and clinical trial are outlined in the Pharmacovigilance Plan for this study.

## 8. STUDY DRUG MATERIALS AND MANAGEMENT

### 8.1 Study Drug

Study drug refers to lasmiditan and matching placebo.

Lasmiditan drug product is a tablet containing 50 mg, 100 mg or 200 mg of lasmiditan (as free base). The tablet is white, film coated, and round with no markings. Lasmiditan drug product is for oral administration.

Lasmiditan hemisuccinate active pharmaceutical ingredient (API) was manufactured by Produits Chimiques Auxillaires et de Synthèse (PCAS), [name]. The drug product was manufactured by Aptuit (Verona) Srl [name] and contains the following inactive excipients: CCI

The placebo tablets were also manufactured by Aptuit (Verona) and contain the following inactive excipients: CCI

The placebo tablets match the active tablets in size, shape and appearance.

Each dose will consist of two tablets for the treatment of a single migraine attack and two tablets for use as rescue medication or as treatment of recurrence of migraine.

- Lasmiditan 50 mg dose – one 50 mg lasmiditan tablet and either one lasmiditan 100 mg matching placebo, or one lasmiditan 200 mg matching placebo.
- Lasmiditan 100 mg dose – one 100 mg lasmiditan tablet and either one lasmiditan 50 mg matching placebo, or one lasmiditan 200 mg matching placebo.
- Lasmiditan 200 mg dose – one 200 mg lasmiditan tablet and either one lasmiditan 50 mg matching placebo, or one lasmiditan 100 mg matching placebo
- Placebo – one 50 mg lasmiditan matching placebo and one 100 mg matching placebo, or one 50 mg lasmiditan matching placebo and one 200 mg matching placebo or one 100 mg lasmiditan matching placebo and one 200 mg matching placebo.

### 8.2 Study Drug Packaging and Labeling

All study drug will be provided as individual dosing cards containing 2 doses. In the card, each tablet will be contained within an individual blister pack. There will be a total of 4 blisters per card. The doses will be separately designated either for initial treatment or for rescue or recurrence.

All study drug will be labeled with:

- Protocol number
- Sponsor's name and address
- Investigational New Drug statement
- Subject's initials and study ID number
- Instructions for use and storage

### 8.3 Study Drug Storage

All study drug should be stored at room temperature.

### 8.4 Study Drug Preparation

No preparation will be required.

### 8.5 Administration

Subjects will be screened outside a migraine attack. The study drug will be dispensed to the subject during **Screening/Visit 1** with instructions to treat an acute migraine attack only after their eligibility has been confirmed by the site. Each subject will be informed of their eligibility via a telephone call within 7 days of the screening visit.

Subjects will be instructed to take both tablets with approximately 4 ounces of water as the FIRST treatment for a new migraine attack providing that:

- the headache is either moderate or severe and has been so for less than 4 hours
- no prior analgesic or acute migraine treatment has been taken to treat the current migraine attack.

Subjects will be instructed to take the second dose (two tablets) if needed with approximately 4 ounces of water for rescue or for recurrence of migraine.

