L100 mg	L100 mg
	L100 mg
	placebo
L200 mg	L200 mg
	L200 mg
	placebo
placebo	placebo

**Telephone Contact:** Within 7 days of **Visit 1** a phone contact must be made by study staff to the subject confirming eligibility in the trial. The subject will be reminded on the use of the diary and on dosing a migraine with study drug. Once eligibility is confirmed, subjects will begin the **Treatment Period**. Subjects considered not eligible will be advised not to take the study drug and an appointment for an **EoS/Visit 2** and the collection of study drug and the diary will be scheduled within one week (7 days) of the confirmation of eligibility phone call.

- **Treatment Period:** Subjects will be asked to treat their next migraine attack within 4 hours of onset providing that the headache severity is at least moderate at that time and not improving. Subjects will record their response to the first dose over the next 48 hours using an electronic diary. Subjects will be asked not to use rescue medication until at least 2 hours after dosing with study drug and completing the 2 hour assessments. If the migraine does not respond at 2 hours, a second dose of study drug may be taken up to 24 hours after the first dose as long as no other rescue medication has been used. If the migraine does respond within 2 hours (headache becomes pain free) but then recurs after 2 hours a second dose of study drug may be taken up to 24 hours after the first dose. Subjects will record their response to a second dose, taken for either rescue or recurrence, for 48 hours in the electronic diary. The total time for recording response to study drug is up to 72 hours depending on whether or not a second dose is used. Subjects are to contact the clinic to schedule **EoS/Visit 2** within one week (7 days) after 1 attack has been treated, or after 8 weeks have passed without treating an attack. The total time on study is approximately 11 weeks.

**Subject Population:** Adult patients with a history of migraine with or without aura.

[figure not shown]
**Number of Subjects:** Approximately 2968 subjects screened and randomized (742 per treatment arm based on the first dose) to ensure that at least 2280 subjects (570 per treatment arm based on the first dose) complete the Treatment Period

**Number of Centers:** Up to 150 centers in the US and rest of world (Western EU, )

**Test Product and Doses:** lasmiditan 50 mg, lasmiditan 100 mg; lasmiditan 200 mg and matching placebo

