## 5.6 Assessments by Study Visit

### 5.6.1 Screening Visit /Visit 1

The following items must be completed and reviewed by the Investigator or sub-Investigator within 14 days:

- Explain the purpose of the study to prospective subjects and obtain written informed consent and HIPAA.
- Document migraine characteristics per IHS criteria (See [Appendix 2](#)).
- Review inclusion/exclusion criteria (See [Sections 6.1](#) and [6.2](#)).
- Document medical history including migraine history and prior treatment and collect demographic information (See [Section 9.1.1](#)).
- Have subject complete MIDAS (See [Section 9.1.1.2](#) and [Appendix 3](#)).
- Record concomitant medications that the subject is taking.
- Document resource utilization (See [Section 9.1.1.3](#)).
- Perform a complete physical examination (including height, weight, and vital signs) (See [Sections 9.1.2](#) and [9.1.3](#)).
- Perform a 12-lead ECG (see [Section 9.1.4](#)).
- Collect blood and urine samples for clinical laboratory tests (hematology, chemistry, and urinalysis; see [Section 9.1.5](#)). The laboratory tests will include serum  $\beta$ HCG for women of childbearing potential (WOCBP). Any woman with a positive pregnancy test will be ineligible for the study. Have subject complete C-SSRS (See [Section 9.1.6](#) and [Appendix 4](#)).
- Review study requirements and instructions on dosing and completing electronic diary (See [Section 9.1.7](#) and [9.1.8](#)).
- Randomize subject through the Interactive Response Technology (IRT) system.
  - For subjects who meet initial screening criteria and are randomized, advise as to when to expect the confirmatory telephone call. Remind subject not to treat a migraine attack with study drug prior to this call.
- Dispense study drug as assigned.
- Provide access to electronic diary.
  - Starting at **Visit 1** and continuing to **EoS/Visit 2**, subjects will be asked daily, how they are feeling and about the use of any concomitant medications.
- Confirm timing of **EoS/Visit 2**.
- Discharge subject.
- A subject may be rescreened only once.

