### 5.6.3 Treatment

Subjects will be allowed up to 8 weeks to treat an acute migraine attack of moderate or severe intensity that is not improving. The attack is to be treated within 4 hours of onset.

- **Prior to dosing the subject will record:**
  - Time of onset
  - Time migraine pain becomes moderate or severe and the severity ((2) moderate or (3) severe) of the pain.
  - Presence or absence (yes or no) of each of the following associated symptoms of migraine: nausea, phonophobia and photophobia.
    - From the list of associated symptoms **present** the subject will identify which **ONE** is most bothersome to them as the MBS.
  - Presence or absence (yes or no) of vomiting.
  - Degree of interference with normal activities
- **Subject will dose with study drug and record time of dosing.**
- Subject will record their response to treatment for 48 hours after dosing with study drug. Total time to record response is up to 72 hours (See [Section 9.1.8](#)).
- Subjects will be asked about any adverse events (if they are feeling anything unusual) and about the use of any concomitant medications.

### 5.6.4 End of Study/Visit 2

The following assessments will be performed:

- Collect any unused study drug and review dosing compliance.
- Collect resource utilization (See [Section 9.1.1.3](#)).
- Collect information on missed days of work and/or school due to migraine.
- Have subject complete C-SSRS (See [Section 9.1.6](#) and [Appendix 5](#)).
- Review any information reported since **Visit 1** regarding AEs and use of concomitant medication and confirm/assess for AEs and use of concomitant medications not already reported.
- Perform a brief symptom-related physical examination if indicated by an AE (See [Section 9.1.2](#)).
- Obtain vital sign readings (See [Section 9.1.3](#)).
- Perform a 12-lead ECG (See [Section 9.1.4](#)).
- Collect blood and urine samples for clinical laboratory tests (hematology, chemistry, and urinalysis) (See [Section 9.1.5](#)). The laboratory tests will include a urine pregnancy test for WOCBP. A positive urine pregnancy test will be confirmed with a serum  $\beta$ HCG test. (The confirmatory test may be run in the local clinical laboratory).
- Subject's participation in study is complete.

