### 9.1.7 Dosing Instructions

Study drug should be administered as the **FIRST** treatment for an acute migraine attack. If the subject has already taken any prior analgesic or acute migraine treatment, he/she is no longer eligible to treat the current migraine attack but may treat a later attack with the study drug.

Subjects will be asked to treat their migraine attack within 4 hours of onset providing that the headache severity is at least moderate at that time and not improving. Subjects will record their response over the next 48 hours using an electronic diary. Subjects will be instructed not to use rescue medication until at least 2 hours after taking study drug. If the subject does not become headache pain free within 2 hours, rescue medication will be permitted after completion of the 2 hour assessments. A second dose of randomized study drug may be taken up to 24 hours after the first dose as long as no other rescue medication has been used. The Investigator will advise each subject as to alternative suitable rescue medication. Triptans, ergots, opioids and barbiturates **MUST NOT** be used for rescue medication within 24 hours of study drug administration. If the migraine responds within 2 hours (headache becomes pain free) but then recurs after 2 hours a second dose of randomized study drug may be taken for up to 24 hours from the first dose.

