### 10.5.1 Primary Analysis

The treatment effect between lasmiditan and placebo will be tested first for the primary endpoint of the proportion of subjects who are headache pain free and the key secondary endpoint of the proportion of subjects who are MBS free at 2 hours in the mITT population between the lasmiditan 200 mg and placebo dose group based on the first dose. The primary analysis will be completed using logistic regression Wald Chi-square test with a basic model including treatment group and region, using a one-sided test at the  $\alpha=0.025$  level of significance.

If the primary analysis is statistically significant (one-sided,  $p<0.025$ ), additional confirmatory hypotheses will be tested on the proportion of subjects who are headache pain free and the proportion of subjects who are MBS free at 2 hours in the lasmiditan 100 mg and placebo

groups followed by the lasmiditan 50 mg and placebo groups.

Headache pain free at 2 hours will be defined as a reduction in headache severity from moderate (2) or severe (3) at baseline to none (0) two hours after dosing with study drug. MBS free at 2 hours will be defined as a 'no' response to the presence of the symptom (either nausea, phonophobia, or photophobia) that was identified as MBS at predose, 2 hours after dosing with study drug.

A qualifying migraine is defined as a migraine treated with study drug within 4 hours of onset.

Subjects taking rescue medication within the first two hours or who fail to record headache severity at 2 hours will be assumed to have no headache response in the mITT and the ITT analyses.

A subject is defined to have used rescue medication within the first two hours post dosing if at least one medication is documented in the rescue medication log in the subject electronic diary for which:

$0 \text{ (min)} < \text{date/ time rescue medication (diary)} - \text{date/ time of dosing (diary)} < 120 \text{ (min)}.$

Subjects who do not provide a headache pain severity rating at baseline or who use other medication prior to the study drug for the study migraine attack will be assumed to have no headache response for the ITT analysis.

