4 ANALYSIS POPULATIONS

The following analysis populations will be defined for this study. Subjects' inclusion in or exclusion from these analysis populations will be finalized prior to study unblinding

Randomized population	All randomized subjects. Subjects will be evaluated by the drug to which they are randomized.
Safety population	All randomized subjects who use at least one dose of study drug, regardless of whether or not they undergo any study assessments. Subjects will be evaluated by the drug they use, not by the drug to which they are randomized, when data indicate a difference.
ITT population	All randomized subjects who use at least one dose of study drug and have any post-dose headache severity or symptom assessments. Subjects are evaluated by the drug to which they are randomized.
mITT population	All ITT subjects who treat a migraine attack within four hours of onset. Subjects will be evaluated by the drug to which they are randomized. The mITT population is the primary analysis population.
PP population	All mITT subjects will be considered per protocol (PP) if they do not have major protocol deviations, enumerated below, which might impact the assessment of efficacy. Subjects will be evaluated by the drug to which they are randomized.

Safety-2nd Dose population	All randomized subjects who were considered in the safety population after the first dose and use a second dose of study drug, regardless of whether or not they undergo any study assessments. Subjects will be evaluated by the drug they use, not by the drug to which they are randomized.
ITT-2nd Dose population	All randomized subjects who were considered ITT after the first dose and use a second dose of study drug and have any post-dose headache severity or symptom assessments. Subjects will be evaluated by the drug to which they are randomized.

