4.2 Exclusions from Per-protocol population

The following protocol deviations are considered major and might impact the assessment of efficacy. These deviations would exclude subjects from the PP population.

- Any violation of the following inclusion/exclusion criteria:
Inclusion criteria:
 2. Subjects with migraine with or without aura fulfilling the International Headache Society (IHS) diagnostic criteria 1.1 and 1.2.1 (International Headache Classification (ICHD)-2004).
 4. MIDAS score ≥ 11 .
 6. History of 3-8 migraine attacks per month (< 15 headache days per month).

Exclusion criteria:

12. Previous participation in this clinical trial.
15. History, within past 12 months, of chronic migraine or other forms of primary or secondary chronic headache disorder (e.g. hemicranias continua, medication overuse headache) where headache frequency is greater than or equal to 15 headache days per month.
16. Use of more than 3 doses per month of either opiates or barbiturates.

The criteria violations above will be identified from entries on CRF page Inclusion/Exclusion Criteria or explicitly recorded in Protocol Deviations log.

- First Treatment with study drug beyond 4 hours after the onset of migraine
- Use of triptans and ergots as concomitant medications within 24 hours of study drug administration. As concomitant medications are entered in the CRF with start dates but not times, this 24-hour period will be identified as the date of dosing and the next day. Use of excluded rescue (concomitant) medications before 24 hours after dosing or use of any early

rescue medication (study drug or not) before 2-hour time point. Cases of early rescue medication use will be identified from e-diary entries. Cases of using excluded rescue medication will be identified from concomitant medications data with an entered indication entry that indicates use for migraine. (A listing of all rescue medications will be generated and reviewed prior to study unblinding, and will be used to evaluate this protocol deviation.) As concomitant medications are entered in the CRF with start dates but not times, the 24-hour period will be identified as the date of dosing and the next day.

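### Protocol 8.5 starts the 4-hour dosing clock when pain becomes moderate or severe; every other dosing window, and the mITT rule, starts it at onset

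*Protocol*

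**What the plan says.** Protocol 8.5 (Administration) sets conditions for taking the first dose. One is that "the headache is either moderate or severe and has been so for less than 4 hours". The time limit attaches to the moderate-or-severe state, so the clock starts when pain reaches that level.

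The other dosing windows start the clock at onset and treat severity as a separate condition:

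- Synopsis, Treatment Period (Protocol 5.5 and SAP 2.1 say the same about timing): "Subjects will be asked to treat their next migraine attack within 4 hours of onset".
- Protocol 5.6.3: "The attack is to be treated within 4 hours of onset".
- Protocol 9.1.7, Dosing Instructions: "Subjects will be asked to treat their migraine attack within 4 hours of onset".

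The analysis rules also use onset:

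- Protocol 10.5.1: "A qualifying migraine is defined as a migraine treated with study drug within 4 hours of onset". The Protocol mITT population (10.3.1) requires a qualifying attack.
- SAP 4, mITT, the primary population: "All ITT subjects who treat a migraine attack within four hours of onset".
- SAP 4.2, exclusions from PP: "First Treatment with study drug beyond 4 hours after the onset of migraine". The Protocol's own PP list (10.3.1) has no explicit 4-hour item; it relies on a general rule that the subject did not deviate from the protocol.

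At Visit 1, Protocol 5.6.1 tells staff to "Review study requirements and instructions on dosing and completing electronic diary" and refers them to 9.1.7 and 9.1.8. The treat instruction in the eligibility-call text (5.6.2) gives no time limit.

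**The concern.** Section 8.5 is an instruction for taking the drug, not background text. Its clock is looser than the onset clock for any attack that begins mild. A subject told only what 8.5 says could follow it and still dose too late for the primary population. That subject would have been randomized and treated, yet would not count in the mITT test of pain freedom or of the most bothersome symptom (MBS). At stake is a possible, avoidable loss of subjects from mITT and PP, with some loss of power.

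The point concerns the time clock only. On severity, 8.5 is stricter than the SAP, which counts headaches that were mild at dosing (SAP 5.1).

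**Working it through.** **1. Are the two clocks really different?** Yes. Before dosing, subjects record the time of onset and, separately, the time pain becomes moderate or severe (Protocol 5.6.3 and 9.1.8). SAP 8.5 (Characteristics of Treated Migraine Attacks) calculates time to dosing from each start. Onset therefore cannot be read as the start of moderate pain.

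**2. How far apart are they?** Let m be the hours of mild pain before the headache becomes moderate or severe. Under Protocol 8.5 the latest permitted dose is just under m + 4 hours after onset; under the other rules it is 4 hours. The gap is m. The values of m are assumed, because the documents give no distribution.

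| m (h) | Latest dose under 8.5, hours after onset (just under) | Excess over the onset rule (h) |
|---|---|---|
| 0 | 4 | 0 |
| 0.5 | 4.5 | 0.5 |
| 1 | 5 | 1 |
| 2 | 6 | 2 |
| 3 | 7 | 3 |

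Example: onset 0 h, moderate at 2 h, dose at 5 h. On the 8.5 clock, 5 − 2 = 3 h, below 4, so the condition is met. From onset, 5 − 0 = 5 h, above 4, so the subject is outside mITT and PP.

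**3. What could it do to power?** Inputs from the sample-size sections (Protocol 10.1, SAP 2.2): pain-free rates of 7.4% on placebo, 13.9% on 50 mg, 13.6% on 100 mg and 18.8% on 200 mg; 570 per arm; one-sided 0.025. With p̄ the mean of the two rates,

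power = Φ{ [d − 1.96 × √(2p̄(1 − p̄)/n)] / √([p₁(1 − p₁) + p₂(1 − p₂)]/n) }.

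For 100 mg at n = 570: d = 0.062 and p̄ = 0.105. The null standard error is √(2 × 0.105 × 0.895/570) = 0.01816. The alternative standard error is √((0.0685 + 0.1175)/570) = 0.01807. Power = Φ[(0.062 − 0.0356)/0.01807] = Φ(1.46) = 92.8%. This agrees with the plan's figure of more than 90%, as do 94.6% for 50 mg and 99.99% for 200 mg.

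The calculation was repeated with an assumed share of each arm lost from mITT through late dosing:

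| Assumed loss | n per arm | 50 mg | 100 mg | 200 mg |
|---|---|---|---|---|
| 0% | 570 | 94.6% | 92.8% | 99.99% |
| 5% | 541.5 | 93.5% | 91.5% | 99.99% |
| 10% | 513 | 92.3% | 90.1% | 99.98% |
| 20% | 456 | 89.0% | 86.4% | 99.93% |

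Put the other way, 90% power needs about 182 per arm for 200 mg and about 512 for 100 mg by the same pooled formula. The margin at 570 is large for the first and about 58 subjects (10%) for the second.

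MBS power was not recomputed, because the plan reports simulated power without the underlying MBS-free rates. The plan's own average for 200 mg under its most conservative scenario is 71%, so there is no spare margin there.

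**The case against.** The strongest reply is that 8.5 does not stand alone. Sections 5.5, 5.6.3 and 9.1.7 bind in the same protocol, and pain cannot have been moderate or severe for longer than the attack has lasted. Any dose within 4 hours of onset therefore also meets the 8.5 clock. Read together, the onset rule governs, and the subject in the example has deviated from the protocol. The section titled Dosing Instructions has the right rule, Visit 1 training refers to it, and no subject card or diary prompt taken from 8.5 appears in the documents. All of that stands. It makes actual exclusions possible rather than shown. It does not make the bullet correct: if the onset rule governs, the 8.5 clock adds nothing, and its only practical effect is to mislead someone who works from that section.

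The analysis side is also well covered. Late dosers with any post-dose severity or symptom assessment stay in ITT, where the primary and key secondary analyses are also run (SAP 11). They have their own subgroup tables (SAP 4.3 and 11.8.2), and SAP 8.5 summarizes both time intervals.

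A reader might infer that the primary population is ambiguous, or that SAP 5.1 failed to declare a change. The documents do not support either. The Protocol's qualifying-migraine definition and the SAP mITT both use onset, so the clock did not change and SAP 5.1 had nothing to record.

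**Conclusion.** Wrong as written; minor. The conflict in wording is certain. Its effect on the trial is not: the number of subjects who would meet 8.5 yet dose more than 4 hours after onset cannot be found from the documents, and the reference to 9.1.7 suggests it is small. The 5%, 10% and 20% losses are illustrations, not estimates. Over that range the 200 mg pain-free test is essentially unaffected, while 100 mg power falls from 92.8% to between 91.5% and 86.4%.

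A reader might go further and infer a biased comparison or a threat to the trial's conclusion. Neither follows. The time of the first dose is fixed before the drug can act, under blinding and with the same instruction in every arm, so no difference between arms is expected. The possible cost is fewer subjects in mITT and PP.

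**What to change.** Reword the bullet in Protocol 8.5 to match 9.1.7, for example: *the headache is moderate or severe, is not improving, and it is within 4 hours of migraine onset*. Keep the word onset. A phrase such as the start of the attack could be taken to mean the start of aura, and subjects with aura are eligible. Check any subject instructions drawn from 8.5.

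No new analysis is needed. If dosing has already taken place, the two diary times allow the affected subjects (more than 4 hours from onset, less than 4 from moderate or severe pain) to be counted.

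The cost is one bullet and that check. The small downside is that a subject past 4 hours from onset must wait for a later attack. At 3 to 8 attacks per month (Protocol 6.1), 8 weeks is 56/30.44 = 1.84 months, or about 5.5 to 14.7 attacks. If a week goes to confirming eligibility, 49/30.44 = 1.61 months gives about 4.8 to 12.9. Fewer remain after a skipped attack and not all would qualify, but a later chance is likely.
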